## Highlights

- Examine the feasibility and acceptability of culturally adapted PM+ EP among young populations with high levels of distress in Afghanistan.
- Assess mental health symptoms reduction and behavioural change among Afghan youth.
- Discuss the process of culturally adapting evidence-informed mental health interventions for Afghan populations.

### 1. Background and Rationale

An estimated 85% of Afghanistan's population have experienced or witnessed at least one traumatic event that has left them in psychological distress, with most averaging four events (Human Rights

Watch, 2018). The psychological disturbance from decades of conflict, is only accentuated by high rates of poverty, and the cultural and structural barriers to mental health and health care. Similarly, recent assessments have illustrated that more than a third of children in Afghanistan have experienced some psychological distress due to loss of loved ones, and the constant threat of death and illness around them; oftentimes manifesting into mental health conditions, such as Post-Traumatic Stress Disorder (PTSD), anxiety and depression (Qamar et al, 2022). Children and adolescents are more vulnerable to developing mental health symptoms due to their ongoing emotional and social development (Lewis et al, 2019). In fact, children who are subjected to violence and conflict are at a high risk of developing cognitive and social difficulties (Neto et al, 2022). In a study of 1011 adolescents in Afghanistan, 22.2% met the criteria for a probable psychiatric disorder and 18.0%, 4.8%, and 23.9% met the criteria for emotional concerns, conduct problems, and PTSD, respectively (Panter-Brick et al, 2019). In another study, it was found younger age was itself a risk factor for developing mental health disorders (Alemi et al, 2018).

Researchers have identified a link between the negative mental health effects caused by a lack of social cohesion within Afghanistan's insecure context, and a high level of violence (Abasi, 2008). They found mental health problems are a key contributor to violence, in combination with other impacts of adversity faced in Afghanistan. Whilst research on child development shows, in turn, experiences of violence can lead to mental health issues developing (Shoib et al, 2022). In Afghanistan, children are particularly prone to being victimized by persistent violence; one cross-sectional study found 71% of children experienced physical violence across 2017 (Shoib et al, 2022). Furthermore, subsequent vulnerability, anxiety, and psychological distress all have a detrimental impact on the neurocognitive development of children and have resulted in widespread mental health issues in the country (Shoib et al, 2022; Kovess-Masfety et al, 2021). Further studies conducted in Afghanistan have found that vulnerable youth who experience distressing experiences are more likely to join non-state armed groups, and that without effective rehabilitation and mental health support, violence is likely to be a reoccurring issue (Schwartz, 2020).

Children in Afghanistan face numerous obstacles to achieving stable mental health, including poverty, lack of stability, and persistent violence. This can in turn contribute to adverse childhood experiences, such as difficulty maintaining relationships, difficulty regulating emotions, and difficulty concentrating (Jones et al, 2020). Without support to help them regulate their emotions, in an attempt to manage high stress levels, some children may resort to unhealthy coping mechanisms, such as being violent, withdrawing from society, or taking drugs (Catani, 2018; Hadid et al, 2019). Living in an environment where there is a constant state of conflict exacerbates mental health symptoms. This combined with the cultural stigma around mental health, lack of inclusion, and lack of mental health literacy, prevents enabling environments to form where support is available.

In Afghanistan, much of the interpersonal violence is concentrated in the most conflict-affected areas including Central Highlands, western, and southern regions, where health and justice infrastructure are weak (Ferguson, 2018). Such socioeconomic risk factors as poverty, unemployment, lack of education, and exposure to violence have also been found somewhat associated with attitudes towards violence, with a higher acceptance of violence among populations most affected by adversity (Li et al, 2018). Identifying mechanisms that minimise this risk of violence is critical in developing violence prevention programs and interventions. One study, designed to analyse the relationship between childhood exposure to violence and adolescent conduct, revealed that children who are

exposed to violence and victimization before the age of ten have an increased risk of enacting violent behaviours, and that exposure to violence is a demonstrated predictor of violence in adolescents (Weaver et al, 2011). Further research indicates that persistent violence in Afghanistan is both a catalyst and a consequence of mental health disorders (Nascimento et al, 2022). Thus, by better understanding this relationship between mental health symptoms and violence, we can support the development of preventative interventions that work to effectively prevent and mitigate violence for this particular population.

Afghanistan's mental health system has been historically weak, with decades of underinvestment, limited specialist availability, and a fragmented approach to care (Rahimi-Movaghah et al, 2014). In response to these challenges, the Basic Package of Health Services (BPHS), introduced in 2003, sought to integrate mental health into primary healthcare, aiming to improve accessibility in a country where psychiatric services were previously centralized in just a few urban centers (Trani et al, 2010). This integration marked a significant step forward, ensuring that mental health care was included in public health facilities nationwide. However, despite its ambitious goals, the BPHS faced several obstacles. While it expanded the availability of psychological support within primary healthcare facilities, the actual implementation remained inconsistent, largely due to inadequate funding, a shortage of trained mental health professionals, and competing healthcare priorities (Ventevogel et al, 2013). Many BPHS clinics lacked the resources and staffing to provide meaningful psychological interventions, often reducing mental health care to the prescription of psychotropic medications by undertrained general practitioners (Scholte et al, 2004). Additionally, stigma and cultural misconceptions surrounding mental illness limited community engagement, preventing many from seeking available services (Rahimi-Movaghah et al, 2014). The collapse of international funding following the Taliban takeover in 2021 further weakened the system, leaving mental health services even more under-resourced (HRW, 2022). Given these limitations, the need for alternative, community-based, and culturally adapted mental health interventions is clear. Programs that train lay health workers in structured, evidence-based approaches - such as Problem Management Plus (PM+) - offer a feasible way to bridge the current service gaps. PM+ is an evidence-based low intensity psychological intervention developed by the World Health Organization (WHO), designed for adults impaired by distress due to exposure to conflict and adversity. The intervention seeks to introduce strategies to help people problem solve, manage stress, build resilience, and reflect on behaviors and actions in real time. It has been tested with favorable outcomes amongst refugee and LMIC populations (Schafer et al, 2023). 'Emotional Processing' (EP) is a newly developed component introduced in session 3 that helps participants process significant life memories—two positive and one distressing—by discussing the emotions, thoughts, and future perspectives associated with them, using a jigsaw puzzle metaphor. Its goal is to reduce emotional intensity around these memories through structured reflection and emotional expression (Alozkan Sever et al, 2021). This pilot study will analyse the applicability of PM+ EP in a country of origin, in this case, Afghanistan. By providing interventions that align with local cultural frameworks and strengthening community engagement, these programs have the potential to address both psychological distress and associated risk factors for violence among young people in Afghanistan (Alem et al, 2008).

This pilot study will assess the feasibility, acceptability, and safety of implementing the culturally adapted PM+ EP among a novice population in Afghanistan. The study will examine the process of cultural adaptation and implementation, evaluating whether these interventions are practical and well-received by the target population. As a secondary objective, the study will explore the association

between mental health symptoms—such as depression, anxiety, aggression, and impaired functioning—and experiences of violence among young people in Afghanistan. Using our chosen instruments, we can examine key factors contributing to violence at baseline and explore how differences in mental health outcomes relate to behavioural change. Ultimately, the findings may inform the development of scalable mental health interventions that support improved mental health outcomes, daily functioning, and a reduction in violence.

## 2. Methods

### 2.1 Design and Setting

The study is a stand-alone project, culturally adapting the existing World Health Organization (WHO) PM+ programme and trialling it with a new subject population - Afghan youth. This pilot RCT will be conducted in a community setting in Afghanistan and the research team will be a mix of researchers attached to the Vrije Universiteit (VU) Amsterdam, and field researchers in Afghanistan working with non-profit Peace of Mind Association (PoMA).

This study is a pilot randomized controlled trial (RCT) which involves assessing the feasibility and acceptability of culturally adapted PM+ with an Emotional Processing (EP) module (PM+ EP), and exploring the relationship between mental health symptoms and behavioural change. Self-report assessments will be conducted at three points during the study; prior to delivering the intervention (T1), directly post-intervention (T2), and 3 months-post intervention (T3), and through a qualitative interview conducted at the end of the study.

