## Abstract

**Background:** A large portion of Afghanistan's population, particularly children, has endured prolonged conflict, poverty, and displacement, leading to significant psychological distress. As children grow into adolescence and adulthood, this distress often manifests in mental health symptoms and an increased likelihood of violent behaviours. With limited mental health professionals and strong stigma around mental health in Afghanistan, culturally adapted, evidence-based interventions are needed.

**Objective:** The study aims to explore the feasibility and acceptability of culturally adapted mental health intervention Problem Management Plus with an additional Emotional Processing module (PM+ EP), in reducing psychological distress in young Afghans. The primary objective is to assess the feasibility of delivering this intervention in Afghanistan and its acceptability by the target communities, and the secondary objective is to assess symptom reduction and behavioural change.

**Methods:** This is a pilot Randomized Control Trial (RCT) with participants aged 16 to 30 in Afghanistan. Eligible participants, young Afghans with high levels of distress and impaired functioning - measured by the Kessler Psychological Distress Scale (K10) -, will be randomized to PM+ EP (n=30) or the waiting group (n=30). The participants will be evaluated through self-report questionnaires at three time points; baseline (T1), four weeks later immediately post-intervention (T2), and 3 months post-intervention (T3), and through a qualitative interview (Process Evaluation) at the end of the study. Outcomes will include measures of anxiety and depression (HSCL-25), aggressive behaviours (AGQ), PTSD symptoms (PCL-5), and daily functioning (WHODAS 2.0).

**Results and Conclusion:** This study will assess the feasibility and acceptability of culturally adapted PM+ EP in Afghanistan and explore the relationship between mental health symptoms and violence among young Afghans. It will be the first to evaluate the feasibility of PM+ EP with this population and could pave the way for a large define RCT examining the effectiveness this approach, should the results show promise.

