#### 2.2.2 Sample Size

Since this is a pilot RCT no power calculations have been carried out. The total sample size will be 60 persons, with half of the participants receiving PM+ EP (N=30) and half assigned to the waiting group (n=30). Randomization will be carried out using a random numbers table generated by computerised software. Those participants in the waiting group will be offered the chance to receive the intervention

post-study. The total number included in the study allows us to evaluate the feasibility and acceptability of the intervention and allow for drop-out rates and incomplete data to be omitted. For the Process Evaluation, a non-random sample size of ten people will be interviewed.

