### 2.3 Procedure

Participants receiving PM+ EP will meet their facilitator individually, someone of the same gender, and receive the intervention through sessions conducted over Zoom or a similar platform; mitigating the difficulties around accessing psychological support, and the risks associated with safety of participants and stigma around mental health. Participants will receive six individual sessions of PM+ EP over the period of one calendar month.

All participants will complete four surveys for assessment at study points T1, T2 and T3; The Hopkins Symptom Checklist 25 (HSCL-25) to measure for anxiety and depression (Mollica et al, 1987), The Aggression Questionnaire (AQG) to measure violent behaviours (Buss and Perry, 1992), The Post Traumatic Stress Disorder (PTSD) Checklist for DSM-5 (PCL-5) will screen participants for symptoms of PTSD (Weathers et al, 2013), and cognitive ability and overall ability to function will be measured by WHO Disability Assessment Schedule 2.0 (WHODAS 2.0) (WHO, 2012). The latter has been used in studies looking at PTSD and other trauma-symptoms in low-resource settings, to assess the communities' impaired daily functioning (Hamdani et al., 2020). After the final assessment has been complete, a non-random sample of participants will be invited to partake in an interview – the Process Evaluation -, to gather qualitative data to assess the feasibility and acceptability of the program.

The timeline and frequency at which the instruments that will be used for screening, baseline and post intervention are listed in the table below. Some of the listed instruments have translations in Dari or Farsi (Afghan Persian/Iranian Persian). In case there is no translation, the instrument will be translated and back translated by the research team.

*Table 1. Measure Overview and Timeline*

Assessment Timeline					
Enrolment T0	Allocation	Baseline T1	Post-intervention T2	Follow-up - 3 months Post- intervention T3	Close-out
Enrolment:					
Eligibility criteria	X				
Informed consent	X				
Allocation		X			
Intervention:					
PM+ EP		X	X	X	X
Waiting Group					
Assessment:					
K10	X				
HSCL-25		X	X	X	
AGQ		X	X	X	
DSM-5 (PCL-5)		X	X	X	
WHODAS 2.0		X	X	X	
Process Evaluation					X

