### **3. Analysis**

To evaluate the feasibility and acceptability of the intervention, qualitative analysis will be conducted through interviews with participants and facilitators, in addition, quantitative data will be gathered on mental health symptoms and behavioral outcomes. Qualitative data will be analyzed using ATLAS.ti to explore participant experiences and inform future intervention development. Interview transcripts will be imported into the software for systematic coding. An initial coding framework will be developed both deductively, based on study objectives, and inductively, based on emerging data. Two researchers will independently code a subset of transcripts, refining the codebook through consensus discussions to ensure consistency. All transcripts will then be fully coded, and thematic analysis will be conducted to identify key patterns and relationships. Findings will be used to complement

---

 DSM-5 (PCL-5) in Persian, [Psychometric Properties of the Persian Version of the Posttraumatic Stress Disorder Checklist for DSM-5 \(PCL-5\)](#)

 [WCG Clinical Services: Improving Clinical Trial Quality & Efficiency](#)

quantitative outcomes, providing a deeper understanding of feasibility, acceptability, and potential mechanisms of change within the intervention. To analyse quantitative data, mean differences in subscale scores and total scores between baseline (T1) and follow-up assessments (T2 and T3) will be determined. Linear mixed models will be employed to analyze feasibility and acceptability data, with treatment as a fixed effect, baseline endpoint measurements as covariates, and subjects as a random effect. This approach will allow for the assessment of trends in participant retention, session attendance, and intervention adherence over time while accounting for individual variability.

Feasibility will be assessed through intervention-specific metrics, including recruitment and consent rates, session attendance, assessment completion, protocol adherence, and occurrences of adverse events. Qualitative data collected through Process Evaluation interviews will complement these findings, providing contextual insights and a deeper understanding of the feasibility and acceptability of the program.

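### Table 1 lists Allocation before Baseline T1 and nothing withholds the arm until T1 is submitted, so the self-reported baseline could be answered with the arm known

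*Protocol*

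**What the plan says.** Four places in the protocol bear on the order of baseline and allocation.

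- **Section 2.1** anchors T1 to delivery of the intervention and to nothing else: "Self-report assessments will be conducted at three points during the study; prior to delivering the intervention (T1").
- **Section 2.3, Table 1** has column headings that begin "Enrolment T0 Allocation Baseline T1".
- **Section 2.2.2** says how the sequence is produced: "Randomization will be carried out using a random numbers table generated by computerised software". It does not say when allocation is made or when the participant learns it. On the comparator it says "Those participants in the waiting group will be offered the chance to receive the intervention" once the study is over.
- **Section 3** makes T1 the reference for change: "mean differences in subscale scores and total scores between baseline (T1) and follow-up assessments (T2 and T3) will be determined".

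HSCL-25, AGQ, PCL-5 and WHODAS 2.0 are all self-reported and are taken at T1, T2 and T3. K10 is taken once, at enrolment. No section describes blinding of participants or a step that holds back the arm, and no section places T1 before allocation.

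**The concern.** A participant who is told the arm in a waiting-list trial knows whether treatment starts now or later. Distressed people may answer symptom and aggression questionnaires differently after hearing this, in either direction. If T1 is completed at that moment, it is no longer a pre-randomisation measurement, and the two arms may differ at T1 for a reason other than chance.

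What is at stake is the secondary, exploratory evidence on symptom and behaviour change. A T1 shift that fades by T2 or T3 would appear as a difference in change between arms. K10 cannot replace T1 as the reference for change, because it is not repeated. The order of baseline, allocation and disclosure is trial conduct and belongs in the protocol, so an unseen analysis plan would not normally settle it.

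**Working it through.** **1. Order of events in the text.** Section 2.1 is satisfied whether T1 falls before or after randomisation. Section 2.2.2 gives no timing. The Table 1 headings put Allocation before Baseline T1. The table body does not settle the matter: in the extracted text there are six headings over five mark positions, and the Allocation mark shares a position with the first mark of the four questionnaires. By the headings T1 follows allocation; by the marks the two coincide. Neither reading shows T1 finished before allocation.

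**2. Inputs for an illustration.** From the protocol: 30 per arm. The protocol gives no SD, correlation, dropout rate or effect size, so the following are assumptions:
- a T1 shift of d SD in one arm, with d = 0.1 to 0.3;
- a fraction p of that shift persisting to follow-up;
- a correlation r between T1 and follow-up of 0.5 to 0.7 (0.3 to 0.7 for the adjusted analysis);
- equal SDs at each time point and no true effect.

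**3. Difference in change from T1.** The bias has size (1 − p)d, and SE = √(4(1 − r)/n).
- n = 30, r = 0.5: √(2/30) = 0.258 SD. r = 0.7: √(1.2/30) = 0.200 SD.

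| d = 0.2, n = 30 | Bias (SD) | In SEs (r = 0.5 to 0.7) |
|---|---|---|
| p = 0 | 0.20 | 0.77 to 1.00 |
| p = 0.5 | 0.10 | 0.39 to 0.50 |
| p = 1 | 0 | 0 |

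Values for d = 0.1 and 0.3 are 0.5 and 1.5 times these. If only 24 per arm are followed up (assumption), the SEs are 0.289 and 0.224 SD, and the p = 0 row becomes 0.69 to 0.89 SE.

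**4. Comparison adjusted for T1, shift fully faded.** The bias is about r × d, and SE = √((2/30)(1 − r²)). For d = 0.2:
- r = 0.3: bias 0.06 SD
- r = 0.5: bias 0.10 SD
- r = 0.7: bias 0.14 SD

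At a two-sided 5% level the false-positive rate is about 6% to 12% over this range, against about 10% to 17% for the change contrast.

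**5. T2 or T3 comparison without T1.** If the shift has faded (p = 0), the bias from this source is 0.

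**6. Could it be seen in the baseline table?** The SE of the T1 difference is √(2/30) = 0.258 SD, so the 95% half-width is 2.002 × 0.258 = 0.517 SD. A two-sided 5% t-test would flag a shift of 0.1, 0.2 or 0.3 SD with probability 7%, 12% or 21%. A plausible shift would usually pass as chance imbalance.

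**7. Baseline association of symptoms with aggression** (section 1: "we can examine key factors contributing to violence at baseline"). If both scores shift by d in half the sample, a correlation ρ becomes (ρ + d²/4)/(1 + d²/4). With ρ = 0.40 (assumed) and d = 0.2, this is 0.410/1.010 = 0.406, which is negligible.

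**The case against.** The strongest reply is that nothing in the protocol is misstated. Section 2.1 is correct as it stands, no two sections conflict, and the evidence for the order is the heading row of a table that did not survive extraction intact. Harm needs several steps that the protocol does not state: allocation before T1, disclosure before T1, a change in reporting, and fading of that change. Section 3 does not say that symptom changes will be compared between arms. The sentence that names baseline covariates describes a model for feasibility and acceptability data. These points stand, and they limit the weight of the concern. What they do not remove is that the only order visible in the headings is the less protective one, and that no sentence corrects it.

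Four stronger readings are tempting and are not supported:

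- **That participants will know their arm at T1.** The protocol does not say when the arm is disclosed. If disclosure follows T1, no expectation effect arises.
- **That no analysis could deal with the problem.** Adjustment for T1 reduces the bias of a faded shift to about r × d, and a T2 or T3 comparison that leaves T1 out is free of it.
- **That the main results of the pilot are at risk.** Feasibility and acceptability do not depend on T1 scores in this way.
- **That the timetable rules out the remedy.** The Abstract places T2 "four weeks later immediately post-intervention (T2") and section 2.3 spreads the sessions over about a month. Both are approximate, and drawing from a computer-generated list need not take days.

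**Conclusion.** The point holds as a minor one. The Table 1 headings put Allocation before Baseline T1, section 2.1 requires only that T1 precede treatment, and nothing withholds the arm until T1 is submitted. The schedule therefore permits an unblinded self-reported baseline without establishing that there will be one.

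The consequence is confined to secondary, exploratory between-arm comparisons that use T1, and that such comparisons are planned for symptom change is itself an inference from section 3. The size and direction are unknown. The figure of 0.20 SD (0.8 to 1.0 SE) rests on an assumed 0.2 SD shift in one arm, complete fading, 30 per arm and r of 0.5 to 0.7. It halves if half the shift persists and vanishes if all of it does.

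**What to change.** Place Baseline T1 before Allocation in Table 1. State in sections 2.1 and 2.2.2 that HSCL-25, AGQ, PCL-5 and WHODAS 2.0 are completed after consent and K10 eligibility, and before the allocation is made or disclosed to the participant.

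People who consent but do not complete T1 would then not be randomised (or not be told their arm). Count them under metrics that section 3 already lists: "Feasibility will be assessed through intervention-specific metrics, including recruitment and consent rates, session attendance, assessment completion".

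The cost is small. Randomisation or disclosure waits for T1, and a few more people may need screening to reach 60. No extra visit or instrument is needed.
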